4. Presence of hypertrophic cardiomyopathy
5. Presence of infiltrative/restrictive cardiomyopathy
6. Echocardiographic evidence of moderate or severe aortic or mitral valve stenosis or regurgitation
7. Bioprosthetic or mechanical valves
8. Use of medication that effect folate metabolism (e.g. Methotrexate, pralatrexate)
9. Previously diagnosed phenylketonuria
10. Previously diagnosed BH4 deficiencies
11. End stage renal disease requiring hemodialysis
12. Pre-existing seizure disorder
13. Terminal illness (not including heart failure) with expected survival of one year or less
14. Females who are pregnant or breastfeeding. All females of child bearing age will undergo pregnancy testing prior to randomization.
15. Recent hospitalization within three months.

Source of Participants and Participant Recruitment:

Patient recruitment will occur at the site of the Providence VAMC by echocardiographic database and medical chart search. A population of potential study patients will be generated, which will identify patients with echocardiographic parameters of diastolic dysfunction without evidence of systolic dysfunction. Subsequently, a chart review of the electronic medical record system [CPRS] will be performed on potential patients to evaluate for inclusion and exclusion criteria. Potential subjects will be temporarily recorded in a password protected spreadsheet in a restricted access folder on a VA secure server. Personal identifiers of subjects who do not participate will be deleted from the database. We will be requesting an IRB waiver of HIPAA and informed consent for screening purposes ONLY.

After subjects are identified by screening of the database and chart review, subjects will be sent a letter informing about the study. The letter will contain a return envelope to notify us within 15 days of the mailing date if the subject does not want to be contacted by phone. If we do not receive the refusal letter, subjects will be contacted by telephone and will be provided basic information regarding the study. Patients who are interested in participating will be scheduled for a screening visit.

Study Visits (Total of 7 Study Visits and 5 Telephone Calls)

The study visits will take place in patient exam rooms in either the main hospital (building 1), research buildings 32 or 35.

1. Screening visit:

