At this visit, the study will be explained in detail to the patient, and inclusion and exclusion criteria will be reviewed by the study team members. If the patient meets the eligibility criteria and is willing to participate, written informed consent will be obtained. Following the completion of informed consent, the subjects will undergo a limited history and physical exam.

Blood will be drawn for measurement of basic chemistry panel, complete blood count, fasting lipid panel, liver function tests, and the following biomarkers: BNP, glutathionylated myosin binding protein C, adiponectin, aldosterone, endothelin-1, NT-procollagen III, uric acid, and derivatives of reactive oxygen metabolites (DROM). These blood tests have been examined in various studies as markers of the presence of heart failure, ability to respond to treatment of heart failure, or early diagnosis of heart failure¹¹⁻¹⁵.

Subjects will then receive a weight-based test dose of 10mg/kg (rounded to the nearest hundred) of the study medication (Kuvan®(sapropterin dihydrochloride),) and the subject will be observed with blood pressure and oxygen levels being recorded every thirty minutes for one hour. If at any point during this time period, the subject develops hypotension (Systolic Blood Pressure [SBP] <90 or a drop in SBP >20mmHg with associated dizziness or syncope), hypoxemia (decrease in oxygen saturation to <90% on room air), or any evidence of an allergic reaction (pruritus, rash, hives, Heart Rate>100, abdominal cramping, nausea, emesis, or angioedema), the subject will not participate further in the study. Subjects experiencing any of the above symptoms will receive appropriate monitoring and clinical care, potentially including hospital admission, supplemental oxygen, IV fluids, until they are stabilized.

The patients who tolerate the test dose will complete the Kansas City Cardiomyopathy Questionnaire and receive a baseline echocardiogram.

Informed Consent Procedure:

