Members of the investigator team will explain the study to the potential participants and answer any questions that they may have regarding the study protocol. The investigator will make it clear that the protocol is research as well as voluntary and that declining participation will in no way affect further evaluation or access to clinical care. Participants will also be informed that they may withdraw their consent at any point throughout the study. Patients will be given adequate time to read the consent form and discuss its contents with research personnel before signing the consent form. They will also be provided with a phone number through which adverse events should be reported. Participants will then be asked to sign an IRB-approved written consent document and health insurance portability and accountability act (HIPAA) agreement, which will allow data pertinent to the study to be collected.

Following the completion of informed consent, the baseline visit will be scheduled within one week of study enrollment.

2. Baseline visit:

At this visit, the subjects will undergo a brief interview to assess for recent changes in health status. Cardiopulmonary exercise testing will be performed to establish the subjects' baseline. The patients will then be randomized (in a 1:1 fashion as mentioned above) to either Group 1, who will begin the study by taking the study medication in addition to their current medication regimen, or Group 2, who will begin the study by continuing their current medication regimen without the study medication. The subjects in Group 1 will be provided with their preference of either a supply of 100mg Kuvan®(sapropterin dihydrochloride) tablets or Kuvan®(sapropterin dihydrochloride) in the powder form. This visit will last three hours.

The subjects in Group 1 will be instructed to initiate the study medication at the weight-based dose of 10mg/kg (rounded to the nearest hundred) with meals (at the same time each day) for one week beginning the following day (day 1). After telephone contact (table 2) with a study team member on day 7, assuming no adverse effects are noted, the patient will be instructed to increase their daily dose to 20mg/kg (rounded to the nearest hundred) with meals (at the same time each day) for the remainder of the study period. The subjects in Group 2 will not be started on the study medication until after the 'wash-out period' as described in the study design

Study Drug:

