12 week visit (three hours)- Brief history and physical exam, Kansas City Cardiomyopathy Questionnaire, labwork for biomarkers (as documented above), chemistry, lipid, and liver panels, BNP, echocardiogram, and CPET testing.

13 week visit (thirty minutes)- Patients will be crossed over to the second arm of the study. They will receive a brief history and the second group will be provided with a supply of Kuvan®(sapropterin dihydrochloride) tablets or powder.

19 week visit (thirty minutes)- Brief history and physical exam.

25 week visit (three hours)- Brief history, Kansas City Cardiomyopathy Questionnaire, labwork for biomarkers, chemistry, lipid, and liver panels, BNP, echocardiogram, and CPET testing.

Telephone calls will be made at week 1, 3, 9, 16, and 22 to assess for patient compliance, provide any necessary support, and screen for side effects.

	Screening Visit	Baseline Visit	Week 1	Week 3	Week 6	Week 9	Week 12	Week 13	Week 16	Week 19	Week 22	Week 25
Contact	Clinic	Clinic	Tel	Tel	Clinic	Tel	Clinic	Clinic	Tel	Clinic	Tel	Clinic
Limited History/Physical	x				x		x	x		x		x
Assess Medication Compliance					x		x			x		x
Labwork	x						x					x
Echo	x						x					x
CPET		x					x					x
KCCQ	x						x					x
Exacerbation History		x	x	x	X	x	x	x	x	x	x	x
Adverse Event Monitoring			x	x	X	x	x	x	x	x	x	x

Table 1. Follow-up Clinic Visits, telephone calls, and schedule of studies. CPET, cardiopulmonary exercise stress test; KCCQ, Kansas City Cardiomyopathy questionnaire; Tel, telephone contact; Labwork: basic chemistry panel, complete blood count, lipid panel, liver function tests, and the following biomarkers: BNP, glutathionylated myosin binding protein C, adiponectin, aldosterone, endothelin-1, NT-procollagen III, uric acid, DROM

Subject Reimbursement:

Subjects will be reimbursed for every visit they attend. Attendance to visits 1 and 2 (screening and baseline visits), as well as visits 4 and 7 (all three hour visits) will be reimbursed fifty dollars. Attendance to visits 3, 5, and 6 will be reimbursed twenty-five dollars.

Specific Study Procedures:

Questionnaire: The Kansas City Cardiomyopathy questionnaire will be used and is attached (Appendix B).

Echocardiogram: Transthoracic echocardiography uses ultrasound technology to evaluate heart structure and function. Measurements to be collected include:

1. Tissue Doppler Index (Septal and Lateral E')
2. E Velocity
3. E/E' ratio
4. E/A Ratio
5. Pulmonary Vein Tracing (S/D Ratio, A-AR duration, AR Velocity)

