6. Deceleration Time
7. Pulmonary artery systolic pressure
8. Right Ventricular Function (assessed by TAPSE)
9. Left Ventricular Mass
10. Left Atrial Volume Index
11. Longitudinal Strain
12. Circumferential Strain
13. Strain Rate

All echocardiograms will be reviewed by two independent echocardiographers.

Cardiopulmonary exercise test:

Cardiopulmonary exercise testing is a test of a subject's maximal exercise capacity. This test will be performed at the Providence VAMC on clinical VA owned equipment. This test will be performed on a bicycle in the presence of a physician. The subject will wear nose clips, and will breathe through a mouthpiece connected to a metabolic machine, which will measure factors including oxygen consumption, CO₂ production, volume of air per breath, and respiratory rate. The patient will also be monitored by EKG leads demonstrating the heart rate and rhythm. The patient will then exercise at increasing levels of resistance (increasing intensity of exercise) according to a protocol until the protocol is completed or the patient can no longer exercise. The maximal value for oxygen consumption (VO₂ max) will be recorded, along with other exercise parameters such as the respiratory quotient (ratio of O₂ consumption to CO₂ production), the ventilatory equivalent ratio for carbon dioxide (Ve/VCO₂), and the dead space to tidal volume ratio.

Laboratory testing:

This will be done by a trained phlebotomist who will draw blood samples from a venipuncture site, typically from the subject's arm. The laboratory tests drawn include a basic serum chemistry panel, lipid panel, liver panel, and biomarkers associated with diastolic dysfunction (as described above). All labs, besides the diastolic dysfunction biomarkers are basic labs and will be drawn and handled at the Providence VA per VA laboratory protocol. The labs associated with diastolic dysfunction will be drawn by phlebotomy but handled by the protocol below:

- 1) Draw six lavender top (EDTA) tubes (2 tablespoons each). These tubes will be maintained at 4°C.
- 2) 1cc of whole blood will be aliquotted from the 1st tube and transferred into the plain orange-screw-top cryo tubes.
- 3) Then, the tube will be balanced and centrifuged at 2000g for 10 min using refrigerated centrifugation.
- 4) 1cc plasma to orange top cryo tubes and stored at -80°C freezer until use. This blood will be stored in [name] (co-investigator) storage area

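### The pregnancy-test deadline in exclusion criterion 14 falls after the first dose of study drug

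*Combined protocol and SAP*

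**What the plan says.** Item 14 of the Exclusion Criteria excludes pregnant and breastfeeding women and adds: "All females of child bearing age will undergo pregnancy testing prior to randomization".

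Under Study Visits, the screening visit covers review of the eligibility criteria, consent, a limited history and examination, and a blood draw. Then: "Subjects will then receive a weight-based test dose of 10mg/kg (rounded to the nearest hundred) of the study medication". The questionnaire and echocardiogram follow for those who tolerate the dose.

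The interval to the next visit is given under Informed Consent Procedure: "Following the completion of informed consent, the baseline visit will be scheduled within one week of study enrollment". Randomization is part of that next visit, after the exercise test.

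Two later passages bear on the point. Therapeutic risks states that the drug is untested in pregnancy and that the risks to mother and fetus are unknown. Protection against risk says that women of reproductive age will be tested before they receive study drug, and refers to the exclusion criteria for this.

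**The concern.** A deadline fixes the latest acceptable time for a procedure. For a test meant to keep an untested drug away from pregnant women, the latest acceptable time is before the first dose. Criterion 14 ties the test to randomization, and in this trial randomization is not when drug exposure begins. The test dose comes one visit earlier and goes to subjects later assigned to either sequence.

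A test done at the time criterion 14 allows could therefore reveal a pregnancy only after the woman had already taken the drug. The protocol sets the safer timing elsewhere, but not in the eligibility rule or in the visit steps that staff follow on the day.

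**Working it through.** There is no plan figure to reproduce. The check puts the procedures in order and reads the relevant passages side by side.

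**Order of events** (Screening visit, Informed Consent Procedure, Baseline visit)

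1. Screening: eligibility review, then consent.
2. Screening: history, examination and blood draw.
3. Screening: 10 mg/kg test dose, the **first exposure**.
4. Screening: questionnaire and echocardiogram.
5. Baseline: exercise test.
6. Baseline: randomization, the **criterion 14 deadline**.
7. The following day: Group 1 starts daily dosing.

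The deadline (step 6) falls one visit after first exposure (step 3).

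**Timing.** Assume that enrollment is the day of consent and test dose, and call it day 0.

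- Randomization, within one week of enrollment: at most day 7.
- Group 1's first daily dose: at most day 7 + 1 = day 8.
- Latest test that criterion 14 allows, relative to first exposure: up to 7 − 0 = 7 days after it.

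**Size of the exposure.** Test dose relative to maintenance dose: 10 / 20 = 0.5.

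**Where the test is called for.** Two sentences in the available text require a pregnancy test: one in criterion 14, one in Protection against risk. A test done between steps 3 and 6 would comply with the first and breach the second. A test done before step 3 would satisfy both.

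**Whether the procedural text closes the gap.** None of the three laboratory lists (0 of 3) names a pregnancy test:

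- Screening visit: "Blood will be drawn for measurement of basic chemistry panel, complete blood count, fasting lipid panel, liver function tests, and the following biomarkers", followed by BNP and the other heart-failure markers.
- Table 1 legend: "Labwork: basic chemistry panel, complete blood count, lipid panel, liver function tests, and the following biomarkers", followed by the same markers. The table has no pregnancy-test row either.
- Laboratory testing section: "The laboratory tests drawn include a basic serum chemistry panel, lipid panel, liver panel, and biomarkers associated with diastolic dysfunction (as described above".

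These lists are limited evidence. A urine test might not appear in a list of blood work, the last list is not worded as exhaustive, and Table 1 also leaves out consent, the test dose and randomization. The ordering argument does not depend on them.

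**The case against.** The strongest reply is that the protocol already handles this. Protection against risk requires testing before study drug, which plainly includes the test dose. Criterion 14 gives only a latest time, so one early test meets both rules. This stands: the defect is an inconsistency in timing, not a missing safeguard. It does not cure an eligibility rule whose own deadline is too late, particularly when the stricter sentence sends the reader back to that rule. The cross-reference can be read as pointing only to the exclusion of pregnant women and not to the later deadline. Even so, the stricter timing is stated in one sentence of the risk section and in none of the visit steps.

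A second reply is that the exclusion criteria are reviewed at screening, before the dose. That is so, and the review could prompt a test. But it comes before consent and names no test. It would exclude a known pregnancy; an unrecognized one could pass.

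A third reply is that testing earlier lengthens the gap to Group 2's daily dosing, which starts at week 13. Counting weeks from baseline, the gap becomes up to 7 + 91 = 98 days (14 weeks). A test on the day of randomization already leaves 91 days (13 weeks), so the change adds at most one week. The contraception and stop-drug instructions in Protection against risk partly cover that period.

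Finally, the addendum on privacy, security and safety, to which the protocol refers, was not available and might schedule the test. Criterion 14 would still conflict with Protection against risk.

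**Conclusion.** The concern holds. Criterion 14's deadline falls after first exposure, and neither the visit text nor Table 1 carries the earlier timing that Protection against risk requires. A woman could be dosed untested in compliance with criterion 14 and the screening steps, though not with Protection against risk.

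The practical size is modest: a single dose at half the maintenance level. The 7-day figure rests on treating enrollment as the day of the test dose, because the protocol does not define enrollment. The number of women affected cannot be calculated, since the sex and age mix of the 30 subjects is not stated; it is probably small. Sample size, power and the efficacy analysis are untouched. This is a participant-safety correction that should be made, and the conclusion is limited to the text available.

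**What to change.** Make three wording changes:

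1. In criterion 14, set the deadline as before the screening test dose, identified as first study-drug exposure, in place of randomization.
2. In the screening-visit description, after consent, add a pregnancy test for women of child-bearing age and require a negative result before the test dose is given.
3. In Table 1, show the test in the Screening Visit column.

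The test is already planned, so none is added; it moves earlier by at most about a week. It could then precede randomization by up to 7 days and Group 1's first daily dose by up to 8. The current text already permits those gaps, because criterion 14 sets no earliest time and Protection against risk, read plainly, already calls for a test before the test dose.

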Kuvan®(sapropterin dihydrochloride) has not been tested in pregnant women, and there may be unknown risks for pregnant women and for their developing embryo, fetus, or unborn child. The package insert for Kuvan®(sapropterin dihydrochloride) is included in Appendix C.

Protection against risk

Study personnel will be fully trained and credentialed in human subjects protection. Study ID numbers will not include PHI. All research data which will be kept in locked cabinets or password protected files on VA servers.

Risks from cardiopulmonary exercise testing will be minimized by supervision of testing by an attending physician, fellow/resident, or trained technicians at VA Providence with emergency equipment readily available. Patients will be encouraged to exercise to their symptomatic limits, if there are any signs of medical instability, the physician will end the test before the symptomatic endpoint is achieved.

Phlebotomy will be performed by trained phlebotomists.

Females of reproductive age will undergo pregnancy testing prior to receiving the study drug as per the previously noted exclusion criteria. Female subjects will be instructed to use an effective form of contraception during the study period. If any female subjects become pregnant during the study, they will immediately stop taking the study medication and inform their study physician.

Social Risk:

There is a mild risk of inadvertent loss of confidentiality if the computer files or paper files where the patient protected health information or identifiers are breached by vandalism or when regulatory agencies or committees at Providence VAMC or Lifespan reviews the patient records. This risk will be minimized by assigning a study patient ID and saving all protected health information separate from patient files that contain the key with the identifiers. This key will be saved in a password protected file. All paper forms (informed consent, data collection forms, study binders) will be saved in a locked cabinet within [name] office. Only study personnel will have access to these files.

Potential benefits of research to human subjects and others

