All serious adverse events (SAEs) and pregnancy reports whether or not considered drug-related should be reported to BioMarin Pharmacovigilance within 24 hours of receipt by the investigator/sponsor by using the FDA 3500A (MedWatch Form). Clinicians should not wait to collect additional information that fully documents the event before notifying BioMarin's Pharmacovigilance Department of an SAE or pregnancy. BioMarin may be required to report certain SAEs to regulatory authorities within 7 calendar days of being notified about the event; therefore it is important that clinicians submit additional information requested by BioMarin Pharmacovigilance as soon as it becomes available.

Reporting of SAEs to the IRB will be done in compliance with the standard operating procedures and policies of the IRB and with applicable regulatory requirements.

Follow up visits:

Patients will undergo routine follow up visits as outlined in Table 1 to assess compliance with medication use, changes in symptoms, development of adverse reactions and further data collection.

Monitoring for Adverse Events (AEs)

At the baseline clinic visit and each follow-up contact, subjects are to notify study staff if they experience any change in their medical condition or medications, or have urgent care visits, emergency room visits, or hospitalizations. Study staff will also monitor for interim emergency room visits or hospitalizations through patient notification system in CPRS to ensure timely reporting. The investigator will contact participants if any reported adverse event suggests clinical deterioration warranting immediate medical attention. During the study, if a subject experiences medical problems or hospitalization, the study medication will be continued unless complicated by symptomatic hypotension. If discontinued, it would be resumed once baseline clinical status is confirmed, assuming the event was not felt to be related to the study medication itself.

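### Group 2 starts daily drug at week 13 on a pregnancy test about three months old, and no repeat test is required before dispensing

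*Combined protocol and SAP*

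**What the plan says.** **Timing of the test.** Exclusion Criteria, item 14, says "All females of child bearing age will undergo pregnancy testing prior to randomization". Under Protection against risk the protocol adds: "Females of reproductive age will undergo pregnancy testing prior to receiving the study drug as per the previously noted exclusion criteria". These are the only two statements on when the test is done.

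**Timing of drug.** Every subject takes a single 10 mg/kg test dose at the Screening visit. Randomization is at the Baseline visit, planned within a week of enrollment. Group 1 begins daily dosing the next day. Group 2 waits until after the one-week wash-out, and its supply is handed over at the 13 week visit: "They will receive a brief history and the second group will be provided with a supply of" study drug.

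**What is done around week 13.** The 12 week list is "labwork for biomarkers (as documented above), chemistry, lipid, and liver panels, BNP", with echocardiogram, questionnaire and exercise test; it has no pregnancy test. For week 13, Table 1 marks a limited history and physical, exacerbation history and adverse event monitoring, and no labwork. Data and safety monitoring assigns the Table 3 questions to that visit; they cover medication changes, doctor's visits and hospitalizations, but not pregnancy.

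**Safeguards.** Protection against risk says "Female subjects will be instructed to use an effective form of contraception during the study period" and "If any female subjects become pregnant during the study, they will immediately stop taking the study medication and inform their study physician". Monitoring for Adverse Events says that at baseline and each follow-up contact "subjects are to notify study staff if they experience any change in their medical condition or medications". A pregnancy on treatment must be reported to the manufacturer within 24 hours.

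**The concern.** The protocol excludes pregnant women and tests for pregnancy because, in its own account of the drug, "there may be unknown risks for pregnant women and for their developing embryo, fetus, or unborn child". A single test before randomization serves that purpose for Group 1, which starts daily drug almost at once. The crossover delays the same step by about three months for Group 2, and the test is not renewed.

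What is at stake is detection. Contraception lowers the chance of a pregnancy. Self-report, the stopping rule and the reporting rule act only once a pregnancy is known. A woman in Group 2 who conceived during the control period and had not recognised it would be given daily drug at week 13. Nothing in the schedule would prompt a check, and exposure would run until she noticed.

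**Working it through.** **Inputs**

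- Screening to baseline: 0 to 7 days (Informed Consent Procedure).
- Group 1's first daily dose: 1 day after baseline (Baseline visit).
- First period to the 12 week visit, then a one-week wash-out (Study Design; Follow up visits).
- Visit window: 7 days either way (Follow up visits).
- End of second period: week 25.
- 30 subjects randomized 1:1 (Study Design).

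**The plan's own date.** 12 + 1 = week 13, which agrees with the 13 week visit. From baseline this is 13 × 7 = 91 days.

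**Age of the test at the first daily dose.** The visit for the test is not stated, so take it as done at screening or baseline, and assume Group 2 starts on the day of dispensing.

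| | Test at baseline | Test at screening, 7 days earlier |
|---|---|---|
| Group 1 | 0 + 1 = 1 day | 7 + 1 = 8 days |
| Group 2, nominal | 91 days | 91 + 7 = 98 days |
| Group 2, with window | 91 − 7 = 84 days at the earliest | 98 + 7 = 105 days at the latest |

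The nominal difference between groups is 91 − 1 = 90 days, or equally 98 − 8 = 90 days. With the window, Group 2's test is 12 to 15 weeks old.

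**Does the risk section already require a repeat?** Three statements have to be read together. Item 14 puts the test before randomization. The risk section puts it before study drug, in line with the exclusion criteria already given. The Screening visit gives every subject a first dose of study drug. One test before that screening dose meets both testing statements for both groups, so nothing as written calls for another at week 13.

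**Opportunities.** From week 1 to dispensing, Group 2 has six scheduled contacts (weeks 1, 3, 6, 9, 12 and 13), with no pregnancy test stated at any of them. Planned drug after crossover lasts 25 − 13 = 12 weeks. The next contact after dispensing is the week 16 telephone call, whose Table 2 questions do not mention pregnancy.

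**How many women.** Group 2 has about 30 / 2 = 15 subjects. The documents do not say how many are women of childbearing age. As an assumption, take 0 to 3 such women and a 1% to 4% chance of conception over 13 weeks:

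- lower: 0 × 1% = 0;
- upper: 3 × 4% = 0.12 expected conceptions.

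This counts all conceptions in the period. Those recognised before week 13 would be caught by self-report and the stopping rule, so the relevant number is lower still.

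**The case against.** The best defence is the risk section. A site could read a test before receiving study drug as covering the week 13 supply, and the reference to the exclusion criteria as saying only who is excluded. That reading is possible, but the text does not require it, because the screening test dose is already a receipt of study drug. If a repeat is intended, the same edit is needed to say so. Table 1's silence adds little on its own, since it lists no pregnancy test at any visit, not even the initial one.

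The safeguards are real and deal with recognised pregnancies. Twelve weeks of exposure is an extreme: it needs non-recognition through the contacts at weeks 16, 19 and 22. Group 1 also takes drug for 12 weeks with no repeat test stated, so the contrast between groups is confined to pregnancy status at the start of daily dosing.

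A reader might infer more: that all exclusions go unchecked at week 13, including new use of a folate antagonist (item 8) or a seizure disorder (item 12). The documents do not support this. Medication changes and hospitalizations are asked about at that visit, item 12 covers only a disorder that already exists, and no specific harm is described for either.

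The Protocol Addendum, the package insert and the consent pages are not in the text reviewed and might address testing. Statements of absence here cover the available text only.

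**Conclusion.** The point holds for the pregnancy test alone. As written, Group 2 starts daily drug on a test nominally 91 to 98 days old (84 to 105 with the window), against 1 to 8 days in Group 1, and no repeat is required. This rests on the test being done at screening or baseline and on Group 2 starting on the day of dispensing; if Group 2 starts the next day, as Group 1 does, add one day.

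Severity is low. The expected number of unrecognised pregnancies at week 13 is probably well under the assumed upper figure of 0.12 and may be zero. No estimand, analysis or statistical result is affected. The case for acting is that the protocol itself calls the fetal risk unknown and that the check is almost free at a visit already scheduled.

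**What to change.** At the 13 week visit, before supply is given to Group 2, repeat the pregnancy test in females of childbearing age. Do not dispense if it is positive, and keep the subject in the week 25 assessments where safe. State this in the 13 week visit text and under Protection against risk. Add a pregnancy-test row to Table 1 showing the initial test, placed before the screening test dose, and the week 13 repeat for Group 2. No added re-check of items 8 and 12 is needed.

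The cost is a few inexpensive tests within an existing thirty-minute visit. Rarely, a Group 2 subject would have no treated period, which loses one within-subject contrast. The repeat does not detect a pregnancy that begins after dispensing in either group; that still relies on contraception and the stopping rule.
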